Specific Aim 2: In a subset of patients aged 18-25 years, to measure aPWV and FMD_{BA} during normal vs. reduced (via acute ascorbic acid infusion) oxidative stress, and to measure circulating/urine markers of oxidative stress and inflammation before and after 12 months of oral curcumin or placebo.

Hypothesis 3: Oral curcumin therapy will reduce the rate of kidney growth in children and young adults with ADPKD as compared to placebo.

Specific Aim 3: To quantify TKV measured with MRI before and after 12 months of oral curcumin or placebo.

Impact on the field. This study has the potential to establish a **novel, safe, and easy to deliver therapy** for the treatment of arterial dysfunction, and possibly renal cystic disease, in an understudied population of children and young adults with ADPKD.

Research Strategy

Significance

Autosomal Dominant Polycystic Kidney Disease (ADPKD) and Cardiovascular Disease (CVD). ADPKD is the most common lethal genetic kidney disorder ^{1,2}. While the hallmark of ADPKD is the development and continued growth of multiple renal cysts that result in ultimate loss of kidney function ⁴, the leading cause of death among affected patients is cardiovascular in nature ^{1,2}. The proteins encoded by the PKD-1 and -2 genes, polycystin-1 and -2, are expressed in vascular endothelial cells and smooth muscle cells of all major vessels, resulting in extrarenal manifestations of the disease ²³. There are presently very limited treatment options for the prevention of CVD in patients with ADPKD.

ADPKD in Children and Young Adults. Although often considered to be a disease of adults, ADPKD begins in childhood ³ and can in fact be diagnosed *in utero* ²⁴. Even in children with ADPKD, evidence of CV abnormalities begin to manifest, such as elevated blood pressure and increased left ventricular mass index ²⁵⁻²⁷. There are presently very limited treatment options for the prevention of CVD in adults with ADPKD. Thus, childhood/early adulthood may represent a **critical therapeutic window** to prevent future CV complications.

Vascular Function and CVD. As much as 80% of all CVD is associated with dysfunction and disorders of arteries ⁵. Two of the greatest contributors are the development of vascular endothelial dysfunction, most commonly assessed as impaired endothelium-dependent dilation (EDD), and stiffening of the large elastic arteries ⁶, both of which independently predict of future cardiovascular events and mortality ⁷⁻¹⁰.

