Oxidative Stress-Associated Suppression of EDD and Large Elastic Artery Stiffness. The influence of oxidative stress on FMD_{BA} and aPWV (and carotid artery compliance) will be determined by infusing a supraphysiological dose of ascorbic acid (American Regent Labs) known to scavenge superoxide or isovolumic saline, as used previously by the applicant^{68,93}, and others^{84,94-96}. This procedure is currently safely employed in an NIH-funded, IRB-approved protocol in adults with ADPKD at the University of Colorado Denver. The infusion will be performed only if cannulation in a vein on the dorsal aspect of the contra-lateral hand is successful. 0.075 g ascorbic acid/kg fat-free mass dissolved in 150 mL of saline will be infused intravenously at 5 mL/min for 20 min, followed immediately by a “drip-infusion” at 0.5 mL/min over 60 min. Vascular measurements will be made during the “drip infusion” when peak plasma concentrations of ascorbic acid occur⁸⁴. The difference in FMD_{BA} and aPWV (and carotid artery compliance) during ascorbic acid vs. saline infusion indicates the modulation of EDD and arterial stiffness by oxidative stress^{84,94}. These measures will be performed in the sub-group (18-25 yrs) only.

Markers of Oxidative Stress. Urinary 8-iso-prostaglandin F2 α (8-isoprostane) and 8-hydroxy 2 deoxyguanosine (8-OHdG) will be measured by LC-MS/MS as markers of lipid peroxidation⁹⁷ and oxidative DNA damage⁹⁸, respectively, as oxidative damage is increased ADPKD¹⁷. While Aim 2 is primarily in a sub-group aged 18-25 yrs, these oxidative stress measurements will be performed in all participants (6-25 yrs), as urine can be collected non-invasively.

Inflammatory Markers. Plasma C-reactive protein (immunoturbidimetric method) and plasma interleukin-6 (ELISA; R&D Systems) will be measured by the University of Colorado Hospital as circulating inflammatory markers^{79,99}, as both are increased in ADPKD¹⁶. To minimize the amount of blood collected in children <18 yrs, these measures will only be performed in the sub-group aged 18-25 yrs.

Outcome for Specific Aims 3

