- Tend to ↓ the progression of TKV (adjusted for height), which can be examined further in a longer-duration, larger sample size, future R01 grant

Power Calculations and Statistical Analysis. Power calculations are based on clinically meaningful differences in the primary outcomes (FMD_{BA} and aPWV), limited published literature using curcumin in a healthy older population⁴⁴, and experience of the applicant regarding the variability of the proposed outcomes^{68,69,79}. A sample size of 27 in each group will have 90% power to detect a mean increase in FMD_{BA} of 1.5%, given a standard deviation of 2.0⁶⁸, with $\alpha = 0.025$, adjusted for two primary endpoints. Akazawa et al.⁴⁴ demonstrated in healthy post-menopausal women a ΔFMD_{BA} of +1.5% with curcumin compared to a decrease in FMD_{BA} of -0.2% in controls. Similarly, a sample size of 27/group will have 90% power to detect a mean decrease of aPWV of 100 cm/sec given a standard deviation of 125⁶⁹ with $\alpha = 0.025$, adjusted for two primary endpoints. To account for a potential dropout of 20%, 34 subjects/group will be enrolled.

A sub-sample size of 10 in each group (of 18-25 year olds) will have 89% power to detect a 50% reduction in ΔFMD_{BA} with ascorbic acid (given $\Delta FMD = +3.0 \pm 1.0\%$ with ascorbic acid in the placebo group⁶⁸), with a two-sided $\alpha = 0.05$. Aim 3 will be considered exploratory, thus power was not calculated.

Differences between groups at baseline will be assessed by an independent t-test, and a linear mixed-effects model will be fit to compare curcumin vs. placebo (independent variable) with respect to change in outcomes at 6 and 12 months (dependent variables), with covariates and potential confounders (including puberty) incorporated into the model. This approach will account for the use of multiple time points and is flexible to missing (at random) data. Although I do not expect different responses based on sex or race/ethnicity, and the study is not powered to assess these factors, stratified analysis will be performed and any trends will be noted and studied in a larger follow-up study. Dropouts will be handled using an intent-to-treat analysis.

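### The 89% power for Aim 2 fits a single-time-point comparison, but the only between-arm model is on change from baseline; naming the baseline ascorbic-acid response as a covariate would keep power near or above 89% whatever its 12-month correlation

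*Combined protocol and SAP*

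**What the plan says.** **Power.** Power Calculations and Statistical Analysis sizes the mechanistic sub-study of young adults at 10 per arm, a number which "will have 89% power to detect a 50% reduction in ΔFMD_{BA} with ascorbic acid". The placebo-group response is given as +3.0 ± 1.0, and alpha is 0.05, two-sided.

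**Outcome.** The section on oxidative stress-associated suppression of EDD defines the acute response as the difference between the ascorbic-acid and saline infusions, which "indicates the modulation of EDD and arterial stiffness by oxidative stress".

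**Timing.** Specific Aim 2 begins "In a subset of patients aged 18-25 years, to measure aPWV and"; the other measure is FMD, both are taken under normal and reduced oxidative stress, and the measurements are placed before and after 12 months. The session list agrees: the infusion is done at Session 2 and repeated at month 12. The 6-month visit covers only FMD and aPWV, in local patients.

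**Analysis.** One sentence covers every outcome: a linear mixed-effects model comparing the arms "with respect to change in outcomes at 6 and 12 months (dependent variables"). Covariates and confounders are to be included, but puberty is the only one named. The t-test in that sentence is for baseline differences. Aim 2 has no model of its own.

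**Expected result.** Expected Results words Hypothesis 2 as a contrast after treatment: little ascorbic-acid effect in the curcumin arm, a clear one in the placebo arm.

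**The concern.** The power statement and the analysis text appear to concern different quantities. The power statement describes one acute response per participant, with SD 1.0. The analysis text describes a change over 12 months, whose SD depends on how well the response repeats over a year. The plan gives no figure for that.

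The distinction matters because the acute response is itself a difference of two FMD readings and carries the measurement error of both. Low repeatability is therefore plausible, though no figure in the documents shows it. Aim 2 is the key secondary aim and has 10 participants per arm. If the less efficient analysis were used, a real halving of the oxidative-stress effect could be missed and then read as evidence against the mechanism.

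**Working it through.** **Inputs from the plan:** n = 10 per group; placebo response 3.0; 50% reduction, so difference = 0.5 × 3.0 = 1.5; SD 1.0 (the ± is unlabelled and is read as an SD because that reproduces the stated power); two-sided alpha 0.05.

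**Assumed here:** SD 1.0 in both arms and at both visits; rho, the correlation of a participant's acute response between baseline and month 12, varied from 0 to 0.7; 10 per group analysed.

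**1. The plan's own figure.** Two-sample t-test, 18 df, noncentrality = 1.5 / (1.0 × √(2/10)) = 3.354. Power is 88.7%, which agrees with 89%. The alternatives tried do not match: normal approximation 91.8%, one-sided 94.3%, alpha 0.025 80.9%, paired with n = 10 98.7%.

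**2. Unadjusted change score.** SD of change = 1.0 × √(2(1 − rho)), 18 df. At rho 0.3, for example, SD = √1.4 = 1.183, noncentrality = 1.5 / (1.183 × √0.2) = 2.835, and power is 76.5%. The SD exceeds 1.0 whenever rho is below 0.5.

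**3. Baseline as covariate.** Residual SD = √(1 − rho²), 17 df. With 10 per arm, chance imbalance in baseline also costs precision: the variance of the adjusted difference rises on average by the factor 1 + 1/(20 − 4) = 1.0625. Leaving this out gives figures that are slightly too high (88.5% at rho 0, 91.2% at 0.3, 95.4% at 0.5). The table therefore uses simulation of the fitted model, which includes this cost.

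| rho | Unadjusted change | Baseline-adjusted (simulated) |
|---|---|---|
| 0 | 61.2% | 86.6% |
| 0.2 | 70.8% | 88% |
| 0.3 | 76.5% | 89.5% |
| 0.4 | 82.5% | 92% |
| 0.5 | 88.7% | 94% |
| 0.6 | 94.3% | 97% |
| 0.7 | 98.3% | 99% |

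**4. Which dependent variable.** Let Y0 and Y12 be the two responses. The model Y12 − Y0 = a + b·arm + c·Y0 rearranges to Y12 = a + b·arm + (c + 1)·Y0. The arm effect b, its standard error and its p-value are the same. Once baseline is in the model, change and month-12 value give one test.

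**The case against.** A reader might infer that the 89% is wrong, or that true power is 61-83%. The documents support neither, for four reasons.

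- **The range depends on where rho is cut.** 61-83% is what rho from 0 to 0.4 gives, and it stops just short of 0.5, where the shortfall disappears. Over 0 to 0.7 the unadjusted change score gives 61-98%. Nothing in the plan locates rho.
- **The change model is tied to Aim 2 only by inference.** The sentence is general and refers to 6 and 12 months, and the acute response has no 6-month value. Expected Results and the power sentence both read as a post-treatment contrast. It is therefore too strong to say that the plan commits to a weaker test than the one it powered.
- **Baseline may be intended as a covariate.** It is neither named nor excluded.
- **Reproducing 88.7% does not identify the quantity.** Any two-sample t-test with SD 1.0 gives that figure, including one on change. The wording points to a single acute response, but the source cited for the SD cannot be checked here.

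All four points stand, and they limit the claim. They do not remove it: the analysed quantity and the baseline term are unstated, and at low rho the choice moves power by about 25 points (86.6 − 61.2 at rho 0). If baseline adjustment is already intended, the remedy only writes it down.

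**Conclusion.** This is an improvement available at almost no cost, not a demonstrated error in the 89%. That figure is right for a single-time-point comparison with SD 1.0. Under an unadjusted change-from-baseline analysis it holds only if rho is about 0.5 or more. The chance of missing a true 50% reduction would then be about 39% at rho 0 and 24% at 0.3, against the 11% that the plan implies.

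With the baseline response as a covariate, power is within about 2.5 points of the stated figure at rho 0, reaches it at about 0.3, and is at least as high as the unadjusted change score at every rho from 0 to 0.7. The change score is not itself at fault; what is missing is an explicit baseline term.

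The result rests on SD 1.0 at both visits and in both arms, on 10 analysed per group, and on no other covariates; each further covariate would cost a little more. The primary analysis for Aim 1 is not affected.

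**What to change.** Add one sentence to Power Calculations and Statistical Analysis: for Aim 2, the arms are compared at month 12 on the acute response (FMD on ascorbic acid minus FMD on saline), with the participant's baseline acute response as a covariate. Treat the acute aPWV response in the same way. The dependent variable may be the month-12 response or the change.

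The cost is one model degree of freedom. Both responses are already scheduled, so no visits, participants or measurements are added. The sentence should be fixed before unblinding, so that the choice cannot follow the data.

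If the unadjusted change score is kept, restate the Aim 2 power as a range over rho: about 61% at 0, 77% at 0.3, 89% at 0.5 and 98% at 0.7.

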Adherence. As we expect ~50% of all participants to be from out of state, progress will be reviewed with a monthly phone inquiry of medication supply. Please note, due to the long history and prestige of University of Colorado PKD Center studies, our families have tremendous relationships with our research staff (i.e. investigators and research coordinators). The co-mentor, [name], has successfully employed this approach in previous clinical trials in children/young adults with ADPKD that have included ~50% out of state patients ^{54,56}. We expect the minimal side-effects associated with curcumin to favor adherence. Participants will have powder mailed every 3 months and will also be asked to mail back the bottle for a volume check.

Safety Checks. While adverse events are not anticipated, a safety questionnaire will be administered over the phone monthly. Serum creatinine, ALT and AST will be measured after 1, 6, and 12 months, and for those out of state, will be performed at a local contracted laboratory (Quest). Home pregnancy tests will be required monthly for all girls of possible childbearing potential (\geq Tanner Stage 2). All subjects will be given a digital blood pressure monitor (A&D Medical, UA767) with an appropriately sized cuff and the subject/parent will be instructed in its use. Home blood pressures will be taken monthly and reported during phone safety checks. This approach has been successfully employed previously by the co-mentor, [name] ^{54,56}.

Plasma Curcumin Concentrations will be assessed at baseline and 12 months by liquid chromatography-tandem mass spectrometry (LC-MS/MS) at the University of Rhode Island ⁷⁷. Additionally, curcumin concentrations will be measured by the in red blood cells, the buffy coat, and plasma with the addition of citrate to prevent the degradation of metabolites.

Randomization will be performed by the statistician, using a blocked randomization sequence, with stratification by age group (6-13 or 14-25 yrs).

Outcome Measures. The following measurements will be made at baseline and after 12-months of treatment:

Primary (Functional) Outcomes (Specific Aim 1)

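### Sex and race/ethnicity are examined only by stratified analysis with undefined trends, which does not estimate whether the treatment effect differs between groups; a treatment-by-subgroup term in the planned mixed model would

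*Combined protocol and SAP*

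**What the plan says.** The point is covered by one sentence in the combined protocol and SAP, Approach, Power Calculations and Statistical Analysis. It opens with a disclaimer, "Although I do not expect different responses based on sex or race/ethnicity, and the study is not powered to assess these factors", and then gives the method: "stratified analysis will be performed and any trends will be noted and studied in a larger follow-up study".

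The primary analysis is described just before it: "a linear mixed-effects model will be fit to compare curcumin vs. placebo (independent variable) with respect to change in outcomes at 6 and 12 months". Covariates and confounders, puberty among them, go into that model, but no interaction of treatment with sex or race/ethnicity is named. The section does not define a trend. It gives no race/ethnicity categories, no expected stratum sizes, and no rule for comparing one stratum with another. Under Randomization, age group (6-13 or 14-25 years) is the only stratification factor.

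**The concern.** Whether patients respond differently by sex or race/ethnicity is a question about the difference between treatment effects. A stratified analysis gives one effect per stratum, each with its own error. It gives neither the difference nor the uncertainty of the difference. Entering sex or race as a covariate does not fill the gap, because a covariate adjusts a common treatment effect and does not let that effect vary.

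With small strata, one group can easily look responsive and the other not when the true effect is the same in both. The plan intends to carry such patterns into a larger study, so what is at stake is the quality of the leads passed on. The primary conclusions of this trial are not affected.

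**Working it through.** **Inputs from the plan.** For FMD_BA: "A sample size of 27 in each group will have 90% power to detect a mean increase in FMD", with a difference of 1.5 and SD 2.0, so d = 1.5/2.0 = 0.75. For aPWV: "a sample size of 27/group will have 90% power to detect a mean decrease of aPWV of 100 cm/sec", with SD 125, so d = 100/125 = 0.80. Alpha is 0.025, "adjusted for two primary endpoints"; sidedness is not stated for these endpoints. On enrolment: "To account for a potential dropout of 20%, 34 subjects/group will be enrolled".

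**Assumptions, not in the documents.** Two strata (sexes) of about equal size, 27/2, or about 13 per arm; the same true effect in both; two-sided tests at 0.025 or 0.05; a difference read from significance in one sex only.

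**The plan's own figures.** The dropout step reproduces: 27/(1 - 0.20) = 33.75, rounded up to 34. The 90% power does not reproduce as a two-group comparison. For FMD_BA at two-sided 0.025, n = 2 × [(2.241 + 1.282)/0.75]² = 44.1, or 45 per group. Power with 27 per group is 70% by the normal approximation (67% by the t-test). For aPWV the figures are 39 per group and 76% (73%). That is a separate matter and, as shown below, it does not alter this point.

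**Chance that exactly one sex is significant.** If each stratum has power p, the chance is 2p(1 - p). For FMD_BA, two-sample t-test, 13 per arm per sex:

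| Common true effect | p at 0.025 | p at 0.05 | Exactly one, 0.025 | Exactly one, 0.05 |
|---|---|---|---|---|
| 1.5 (design effect) | 33.4% | 45.1% | 44.5% | 49.5% |
| 0.75 (half) | 9.2% | 15.1% | 16.7% | 25.6% |
| 0 | 2.5% | 5.0% | 4.9% | 9.5% |

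For example, 2 × 0.334 × 0.666 = 0.445. For aPWV at its design effect the chances are 47% and 50%. A simulation of 40,000 trials with strata of 14 and 13 per arm gave 45% and 50% for FMD_BA.

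**Sensitivity.**
- Uneven split, 9 and 18 per arm, full FMD_BA effect, alpha 0.025: powers 0.220 and 0.470, so 0.220 × 0.530 + 0.470 × 0.780 = 0.483.
- Stated 90% power taken at face value: the noncentrality is 2.241 + 1.282 = 3.523 overall and 3.523/√2 = 2.491 per stratum. Power is Φ(2.491 - 2.241) = 0.599 at 0.025 and Φ(2.491 - 1.960) = 0.702 at 0.05. The chance of exactly one is then 48% and 42%.
- Race/ethnicity: the number and size of categories are unknown, so nothing can be calculated.

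**The interaction estimate instead.** With four treatment-by-sex cells of 27/2 = 13.5, SE = SD × √(4/13.5). This gives 2.0 × 0.544 = 1.09 percentage points for FMD_BA and 125 × 0.544 = 68 cm/sec for aPWV. The 95% half-widths are 1.96 × 1.09 = 2.1 points and 1.96 × 68 = 133 cm/sec. Power at two-sided 0.05 for a difference as large as the design effect is Φ(1.5/1.09 - 1.96), about 28%, for FMD_BA and Φ(100/68 - 1.96), about 31%, for aPWV. In the same simulation, with no true difference between strata, the interaction test rejected in 4.7% to 5.2% of trials at the 0.05 level, whatever the size of the common effect.

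**The case against.** The strongest reply is that the plan contains no rule of the kind tested above. It does not say that strata will be tested at a threshold, or that significance in one sex alone will count as a difference. A reader might infer that the plan will show a false subgroup difference almost half the time. The documents do not support that. The 44% to 50% needs the full design effect to be real and equal in both sexes, and it needs a sex split that is nowhere given; the small ADPKD pilot under Preliminary Results lists one male and eight females. It also needs a significance rule that the reader has to supply. All of this stands, and the rate can be given only as conditional.

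The second reply is that the authors disclaim power and send any trend to a later study, so this is ordinary hypothesis generation. That stands as a limit on the consequence. It does not repair the method, because the same sentence passes trends forward without estimating the difference between strata. Nor does reading the raw estimates by eye avoid the problem: with an SE of 1.09, two sexes with identical true effects would differ by 1.5 points or more in about 17% of trials (2 × [1 - Φ(1.5/1.09)]).

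The third reply is that an interaction test would usually miss a real difference. That is true, and it is why the term should be reported as an estimate with its interval and not as a test result.

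**Conclusion.** The concern holds as a modest gap in an exploratory analysis. The plan's only method for asking whether response differs by sex or race/ethnicity does not estimate that difference, and a trend is undefined. If strata were compared by significance, with two similar-sized sexes sharing one true effect on FMD_BA, exactly one sex would be significant in about 44% to 50% of trials at the design effect, 17% to 26% at half of it, and 5% to 10% with no effect. The even split and the significance rule are assumptions of this check. For race/ethnicity no rate follows from the documents. The conclusion does not depend on the sample-size calculation: at the design effect the rate stays between 42% and 50% whether the stated 90% power or the recalculated power is used. Nothing here touches the primary comparison.

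**What to change.** In Power Calculations and Statistical Analysis, replace the stratified-analysis sentence with a statement on these lines:

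- Add a treatment-by-sex term to the planned mixed model, and a treatment-by-race/ethnicity term where the numbers in each category allow. State the visit to which the contrast refers.
- Report the difference in treatment effects with its confidence interval, labelled exploratory.
- Show the stratum estimates for description only.
- Base any lead for a follow-up study on the interaction estimate and its interval, in place of undefined trends.
- State that power for these terms is low and that a non-significant interaction is not evidence of equal effects.

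The cost is a few lines of text and one extra model term per factor, with no new data or visits. The drawback is a wide interval, about ±2.1 percentage points for FMD_BA under an even split, which shows openly how little 27 per group can say about subgroups.
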